6.1 PRIMARY EFFECTIVENESS ENDPOINT

Mean Best-corrected Distance Visual Acuity (BCDVA)

Monocular first eyes in the test group will demonstrate distance (far) visual acuity that is comparable to that of the control group. This endpoint will support that the test lens provides far vision that is comparable to that of a standard monofocal

Mean (logMAR) monocular BCDVA at 4 meters under photopic conditions for first eyes in the test vs. control lens groups at 6 months.

Success Criteria: The mean monocular BCDVA for first eyes in the test group at 6 months will be statistically non-inferior to that of the control by a 0.1 logMAR margin.

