20.3 STUDY ENDPOINT

[REDACTED] will be the primary analysis sets for the primary and secondary effectiveness endpoints.

Primary Effectiveness Endpoint

Mean Best-corrected Distance Visual Acuity (BCDVA)

The primary effectiveness endpoint is the mean monocular best-corrected distance visual acuity at 4 m under photopic conditions at 6 months. The non-inferiority comparison between the IOL groups will be conducted using the two-sided 90% confidence interval on the mean BCDVA difference based on a t-distribution. The mean, SD, median, minimum, maximum and two-sided 90% C.I. will be presented by IOL group. Note that lower logMAR value is a better acuity and a higher logMAR value is a poorer acuity. The null hypothesis is that the mean difference between the test and control IOLs is less than or equal to -0.1 logMAR, with the alternative hypothesis being that the mean difference is greater than -0.1 logMAR. A lower bound of the two-sided 90% confidence interval will be used for evaluation based on a two-sample t-test statistic. The success criterion is that the lower limit of the two-sided 90% confidence interval is above -0.1 logMAR.

$H_0: \mu_c - \mu_t \leq -0.10$ (test is inferior (higher logMAR value) to control)

$H_1: \mu_c - \mu_t > -0.10$ (test is not inferior (lower logMAR value) to control)

where

μ_t = the mean logMAR BCDVA for test group

μ_c = the mean logMAR BCDVA for control group

Secondary Effectiveness Endpoints

[REDACTED]

[REDACTED]

[REDACTED]

[REDACTED]

- [REDACTED]
- [REDACTED]

[REDACTED]

Mean Distance-corrected Intermediate Visual Acuity at 66 cm (DCVA66)

The DCVA66 (first eyes) will be summarized (n, mean, SD, median, minimum, maximum) with the two-sided 95% CI by IOL group. Comparisons of mean DCVA66 between the test and control groups at 6 months will be performed using a two-sample t-test with a one-sided alpha level of 0.025.

The null hypothesis is that the mean monocular DCVA66 logMAR value for eyes in the test group is worse than or equal to that for the control group. The alternate hypothesis is that the mean monocular DCVA66 logMAR value for the test group is better than that for the control group.

$H_0: \mu_c - \mu_t \leq 0$ (test is worse than (higher LogMAR value) or equal to control)

$H_1: \mu_c - \mu_t > 0$ (test is better (lower LogMAR value) than control)

where

μ_t = the mean LogMAR DCVA66 for test group

μ_c = the mean LogMAR DCVA66 for control group

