5 POSTOPERATIVE ANALYSES – PRIMARY/SECONDARY ENDPOINTS

5.1 PRIMARY EFFECTIVENESS ENDPOINT

The primary effectiveness endpoint is the mean monocular first-eye best-corrected distance visual acuity at 4 m under photopic conditions at 6 months. The non-inferiority comparison between the IOL groups will be conducted using the two-sided 90% confidence interval on the mean BCDVA difference based on a t-distribution. The mean, SD, median, minimum, maximum and two-sided 90% C.I. will be presented by IOL

group. Note that lower logMAR value is a better acuity and a higher logMAR value is a poorer acuity. The null hypothesis is that the mean difference between the test and control IOLs is less than or equal to -0.1 logMAR, with the alternative hypothesis being that the mean difference is greater than -0.1 logMAR. A lower bound of the two-sided 90% confidence interval will be used for evaluation based on a two-sample t-test statistic. The success criterion is that the lower limit of the two-sided 90% confidence interval is above -0.1 logMAR.

```
H_o: \mu_c - \mu_t \le -0.10 (test is inferior (higher logMAR value) to control)

H_1: \mu_c - \mu_t > -0.10 (test is not inferior (lower logMAR value) to control)
```

where

```
\mu_t = the mean logMAR BCDVA for test group \mu_c = the mean logMAR BCDVA for control group
```

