5.2 SECONDARY EFFECTIVENESS ENDPOINTS

MEAN DISTANCE-CORRECTED INTERMEDIATE VISUAL ACUITY AT 66 CM (DCVA66)

The first secondary effectiveness endpoint is the mean monocular first-eye distance-corrected intermediate visual acuity at 66 cm under photopic conditions at 6 months. The DCVA66 will be summarized (n, mean, SD, median, minimum, maximum) with the two-sided 95% CI by IOL group. Comparisons of mean DCVA66 between the test and control groups at 6 months will be performed using a two-sample t-test with a one-sided alpha level of 0.025.

The null hypothesis is that the mean monocular DCVA66 logMAR value for eyes in the test group is worse than or equal to that for the control group. The alternate hypothesis is that the mean monocular DCVA66 logMAR value for the test group is better than that for the control group.

```
H_o: \mu_c - \mu_t \le 0 (test is worse than (higher LogMAR value) or equal to control) H_1: \mu_c - \mu_t > 0 (test is better (lower LogMAR value) than control)
```

where

```
\mu_t = the mean LogMAR DCVA66 for test group \mu_c = the mean LogMAR DCVA66 for control group
```

The success criterion is a statistically significantly better mean DCVA66 (lower LogMAR value) for test lens compared to the control lens group ($p \le 0.025$).

case population will also be used in the analysis of BCDVA vs. ISO SPE rate. First-eye data will be the primary analysis for safety endpoints.

SECONDARY SURGICAL INTERVENTION RELATED OPTICAL PROPERTIES OF THE LENS

The counts and percentages of secondary surgical interventions (SSIs) related to optical properties of the lens will be reported by IOL group.

SPE RELATED ADVERSE EVENT VS. ISO SPE RATES

The counts and percentages of SPE-type adverse events will be reported by IOL group. The rate in the test lens group will be compared to the ISO Safety and Performance Endpoints (SPE) rates listed in ISO 11979-7 using two-sided 90% Clopper Pearson Exact confidence interval with no CIs multiplicity adjustment.

Success criteria is that the SPE grid that the lower two-sided 90% confidence limit of the test group is lower than the SPE rate.

MONOCULAR BCDVA VS. ISO SPE RATES

The counts and percentages of monocular BCDVA will be presented by IOL group. The rate in the test lens group will be compared to the ISO SPE grid using two-sided 90% Clopper Pearson Exact confidence interval with no CIs multiplicity adjustment.

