8.1 MONOCULAR BEST-CORRECTED DISTANCE VISUAL ACUITY (BCDVA) AT 4 M

For monocular best-corrected near visual acuity at 4 m (BCDVA), with 100 subjects in each lens group there is over 90% power to conclude non-inferiority in visual acuity between the test and control lens group at two-sided alpha of 0.10 with a non-inferiority margin of 1 line, assuming there is no difference between the IOLs and a standard deviation of 1.2 lines.

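### Is the primary non-inferiority test too lenient because it runs at one-sided 0.05 while the secondary runs at 0.025?

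*SAP*

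**What the plan says.** The primary endpoint is mean monocular first-eye BCDVA at 6 months. Protocol 6.1 sets the aim: the test lens "will be statistically non-inferior to that of the control by a 0.1 logMAR margin". SAP 5.1 gives the decision rule: "The success criterion is that the lower limit of the two-sided 90% confidence interval is above -0.1 logMAR". It also says which limit counts: "A lower bound of the two-sided 90% confidence interval will be used for evaluation based on a two-sample t-test statistic". Protocol 20.3 has the same rule.

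The sample-size text uses the same level. SAP 8.1 states that with 100 per group "there is over 90% power to conclude non-inferiority in visual acuity between the test and control lens group at two-sided alpha of 0.10", for a margin of one line and "assuming there is no difference between the IOLs and a standard deviation of 1.2 lines". Protocol 20.7 says the same.

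For intermediate acuity at 66 cm (DCVA66), SAP 5.2 states that the comparison "will be performed using a two-sample t-test with a one-sided alpha level of 0.025".

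Before the formula, protocol 20.3 and SAP 5.1 put the primary null hypothesis in words: "The null hypothesis is that the mean difference between the test and control IOLs is less than or equal to -0.1 logMAR". The formula that follows is control mean minus test mean. Its label says that the null is the case where the test lens is inferior, with the higher logMAR value.

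**The concern.** Three things catch the eye.

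- The lead claim, that the test lens does not give up distance vision, carries a one-sided 5% error, while the secondary claim carries 2.5%. One would more often expect the primary to be at least as strict. If the two were tested in sequence, the overall one-sided error would be 5%.
- The design is so heavily powered for BCDVA that the looser level seems to gain nothing. If 0.025 costs no power, keeping 0.05 looks like an unforced concession, and the visible text gives no reason for it.
- The verbal null speaks of a difference between test and control. Read as test minus control, a negative logMAR difference favours the test lens. A program written from the words alone would then test the wrong side and let a clearly worse lens pass.

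At stake would be the credibility of the claim that distance vision is comparable to a standard monofocal lens.

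**Working it through.** **Inputs.** n = 100 per group; SD = 1.2 lines; margin = 1 line, given elsewhere as 0.1 logMAR; true difference = 0 (protocol 20.7, SAP 8.1). Degrees of freedom are 2 × 100 − 2 = 198.

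**1. The plan's own figure.** The standard error of the difference is 1.2 × √(2/100) = 0.1697 line. The noncentrality is 1/0.1697 = 5.89. The noncentral t distribution at one-sided 0.05 gives power of 99.9988%, so the stated power of over 90% is true. The secondary also reproduces: noncentrality 0.8/(1.6 × √(2/100)) = 3.54, and power 94.0% at one-sided 0.025.

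**2. The primary at one-sided 0.025.** Power is 99.9953%. The difference is 99.9988 − 99.9953 = 0.0035, or about 0.004 percentage points. With 90 per group, power at 0.025 is 99.98%. For 90% power the exact t calculation needs 26 per group at 0.05 and 32 at 0.025. The arithmetic behind the concern is therefore right when the true difference is zero.

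**3. What the stricter level would change in the decision rule.** The largest observed mean loss that still passes is the margin minus t × SE.

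- 90% interval: 1 − 1.653 × 0.1697 = 0.72 line (0.072 logMAR).
- 95% interval: 1 − 1.972 × 0.1697 = 0.67 line (0.067 logMAR).

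The limit moves by about 0.005 logMAR.

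**4. Behaviour away from zero difference.** For a true loss of d lines the noncentrality is (1 − d)/0.1697. The chance of concluding non-inferiority is:

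| True loss of test lens (lines) | One-sided 0.05 | One-sided 0.025 |
|---|---|---|
| 0 | 99.999% | 99.995% |
| 0.3 | 99.3% | 98.4% |
| 0.5 | 90.2% | 83.4% |
| 0.6 | 75.9% | 65.0% |
| 1.0 (at the margin) | 5.0% | 2.5% |
| 1.2 | 0.24% | 0.09% |

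Every row with a loss below 1.0 line is a lens that the plan itself defines as non-inferior. There the stricter level lowers the chance of a correct conclusion, by 6.8 points at half a line (90.2 − 83.4) and 10.9 points at 0.6 line (75.9 − 65.0). At the margin and beyond it lowers the chance of a wrong one. This is the ordinary exchange between the two kinds of error. A greater SD has a similar effect: at 2.0 lines with no true difference, power is 97.0% against 94.0%.

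**5. Consistency.** The decision rule in protocol 20.3 and SAP 5.1 and the power statement in protocol 20.7 and SAP 8.1 all use a two-sided 90% interval or its equivalent, two-sided alpha 0.10. The comparisons with the ISO SPE rates use two-sided 90% intervals as well. The superiority test on DCVA66 has one-sided 0.025 in both its analysis and its power statement. No test is planned at one level and powered at another.

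**6. Direction.** The phrase about the difference between the lenses fixes no order of subtraction. The same passage says that lower logMAR is better, writes the hypotheses as control minus test, labels the null as the inferior case with the higher logMAR value, and defines both means. The secondary uses the same order. With control minus test, a worse test lens gives a negative difference, and a lower limit above −0.1 is the correct criterion. Only the formula's reading agrees with the label.

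**The case for a change.** The strongest case for a change is this. The test optic is described in protocol 7.1 as slightly extending the depth of focus, so distance acuity is exactly what the primary endpoint must protect. If the stated assumptions hold, 0.05 gains almost nothing. If they fail, the extra alpha mainly helps a lens that has lost some distance acuity to be called comparable. A 95% interval would need no further subjects, and no visible text explains the 90% interval.

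Much of this is fair as far as it goes. The primary error rate is twice the secondary's, the zero-difference power is as stated, and a 95% interval would also have been defensible. But the argument counts passes at 0.5 or 0.6 line as errors, and under a one-line margin they are not. Anyone who finds such losses unacceptable is really questioning the margin, which is a different matter from alpha. A factor of two in false-positive risk is exact only when the true loss equals the margin.

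The missing rationale cannot be held against the plan either. Text at the start of section 20, at the head of the secondary endpoints and around the power statements is redacted, and a reason or a testing order may stand there. The parallel with the SPE comparisons supports only the choice of confidence level, since their success rule works differently.

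On direction, adding the order of subtraction to the verbal sentence would be tidier. That is an editorial matter, because a programmer would have to ignore the displayed hypotheses to go wrong.

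**Conclusion.** The concern does not hold. A one-sided 5% level for the primary is a prespecified choice, carried consistently through protocol and SAP and matched to its own power statement. No visible text requires the primary and secondary to share an alpha. Moving to 0.025 would alter the passing limit by about 0.005 logMAR and would change almost no result if the lenses are equal. If the test lens is slightly worse but within the margin, the move would cost 6.8 points of power at half a line and 10.9 points at 0.6 line. The claim that the looser level buys nothing is thus true only at zero difference. The stated power of over 90% is an understatement but correct. The direction of the test is fixed by the formula and its label.

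These figures rest on 100 evaluable subjects per group, an SD of 1.2 lines and one line equal to 0.1 logMAR, as the documents use them.

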5.2 SECONDARY EFFECTIVENESS ENDPOINTS

MEAN DISTANCE-CORRECTED INTERMEDIATE VISUAL ACUITY AT 66 CM (DCVA66)

The first secondary effectiveness endpoint is the mean monocular first-eye distance-corrected intermediate visual acuity at 66 cm under photopic conditions at 6 months. The DCVA66 will be summarized (n, mean, SD, median, minimum, maximum) with the two-sided 95% CI by IOL group. Comparisons of mean DCVA66 between the test and control groups at 6 months will be performed using a two-sample t-test with a one-sided alpha level of 0.025.

The null hypothesis is that the mean monocular DCVA66 logMAR value for eyes in the test group is worse than or equal to that for the control group. The alternate hypothesis is that the mean monocular DCVA66 logMAR value for the test group is better than that for the control group.

```
H_o: \mu_c - \mu_t \le 0 (test is worse than (higher LogMAR value) or equal to control) H_1: \mu_c - \mu_t > 0 (test is better (lower LogMAR value) than control)
```

where

```
\mu_t = the mean LogMAR DCVA66 for test group \mu_c = the mean LogMAR DCVA66 for control group
```

The success criterion is a statistically significantly better mean DCVA66 (lower LogMAR value) for test lens compared to the control lens group ($p \le 0.025$).

case population will also be used in the analysis of BCDVA vs. ISO SPE rate. First-eye data will be the primary analysis for safety endpoints.

SECONDARY SURGICAL INTERVENTION RELATED OPTICAL PROPERTIES OF THE LENS

The counts and percentages of secondary surgical interventions (SSIs) related to optical properties of the lens will be reported by IOL group.

SPE RELATED ADVERSE EVENT VS. ISO SPE RATES

The counts and percentages of SPE-type adverse events will be reported by IOL group. The rate in the test lens group will be compared to the ISO Safety and Performance Endpoints (SPE) rates listed in ISO 11979-7 using two-sided 90% Clopper Pearson Exact confidence interval with no CIs multiplicity adjustment.

Success criteria is that the SPE grid that the lower two-sided 90% confidence limit of the test group is lower than the SPE rate.

MONOCULAR BCDVA VS. ISO SPE RATES

The counts and percentages of monocular BCDVA will be presented by IOL group. The rate in the test lens group will be compared to the ISO SPE grid using two-sided 90% Clopper Pearson Exact confidence interval with no CIs multiplicity adjustment.

Success criteria is that the upper two-sided 90% confidence limit of the test group is higher than the SPE rate.

[figure not shown]

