10.3 PREOPERATIVE PROCEDURES

All subjects treated in the study must sign the current IRB-approved informed consent form and meet the eligibility criteria. The informed consent form must be signed before any study-specific examinations are performed, and this must be documented in the source documents. An Authorization for Use/Disclosure of Health Information Form (HIPAA authorization) or similar medical treatment privacy law documentation must also be signed.

[REDACTED]

[REDACTED]
 [REDACTED]
 [REDACTED] If a test/exam is required by the protocol but is not part of the routine testing the investigator performs for the cataract evaluation, that test/exam is considered to be study-specific and is not to be done until after the informed consent form has been signed by the subject. Following the informed consent process, completion of the preoperative study exam and determination that the subject meets all of the required entrance criteria (including lens power determination), the subject may be randomized and scheduled for surgery.

As the Informed Consent Form is signed at the beginning of the preoperative study exam, some subjects may not qualify after study-specific testing is performed. Subjects will be considered screen-failures if they do not qualify, or if they qualify but decide not to participate further in the study, or if they decide not to proceed with surgery. These subjects will be exited from the study.

Preoperative testing to be performed for each eye includes the following:

POTENTIAL DISTANCE VISUAL ACUITY

The subject must be capable of achieving Snellen 20/30 or better best-corrected distance vision in each eye after cataract extraction and IOL implantation. [REDACTED]
 [REDACTED]
 [REDACTED]
 [REDACTED]

BEST-CORRECTED DISTANCE VISUAL ACUITY AND MANIFEST REFRACTION

Preoperative manifest refraction is required. Monocular, best-corrected distance visual acuity (BCDVA) is to be measured using a standard Snellen chart or equivalent and must be Snellen 20/40 or worse, with or without a glare source.

KERATOMETRY

Predicted postoperative corneal astigmatism, as measured by keratometry, should be less than 1.00 D. No irregular astigmatism should be present preoperatively. Postoperative astigmatism can be surgically managed to be less than 1 D in each eye.

CONTACT LENS WEAR AND CORNEAL STABILITY

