4 DEMOGRAPHICS AND PREOPERATIVE/OPERATIVE PARAMETERS

Subject demographic data including age, sex, race, iris color and ethnicity will be
presented by IOL group. Age will be categorized by less than 60, 60-69, 70-79 and ≥ 80
years old. In addition, age will be summarized with descriptive statistics. The frequency
distribution of sex, race, iris color and ethnicity will also be tabulated. To ensure
comparable demographic characteristics between groups, statistical testing will be
performed.

Deviations from the proposed statistical guidelines will be substantiated by sound statistical rationale. In this study, unless otherwise indicated, two-sample t-tests will be used for continuous data, Wilcoxon rank sum test for ordinal data and Fisher's Exact test for categorical data.

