8.2 MONOCULAR DISTANCE-CORRECTED INTERMEDIATE VISUAL ACUITY AT 66 CM (DCVA66)

For monocular distance-corrected intermediate visual acuity at 66 cm, with 100 subjects in each lens group, there is over 90% power at one-sided 0.025 alpha to detect a 0.8-line or greater difference in mean visual acuity between the test lens and control lens groups, assuming a standard deviation of 1.6 lines.

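### Both decision tests are valid but leave collected baseline data unused; adjusting for age, preoperative acuity and site is a near-free gain, mainly for DCVA66

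*SAP*

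**What the plan says.** **Primary endpoint (SAP 5.1; Protocol 20.3).** Mean first-eye BCDVA is tested for non-inferiority against 0.1 logMAR: "A lower bound of the two-sided 90% confidence interval will be used for evaluation based on a two-sample t-test statistic". No covariate appears.

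**Secondary endpoint (SAP 5.2; Protocol 20.3).** The comparison of mean first-eye DCVA66 "will be performed using a two-sample t-test with a one-sided alpha level of 0.025". Again no covariate appears. Protocol 20.5 names the two-sample t-test as the general method for continuous variables.

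**Baseline data.** SAP 4 lists age, sex, race, iris color and ethnicity. Protocol 10.3 requires preoperative acuity: "Monocular, best-corrected distance visual acuity (BCDVA) is to be measured using a standard Snellen chart or equivalent". It must be 20/40 or worse, and may be taken with or without a glare source. Randomization follows the preoperative exam (Protocol 10.3) and the documented choice of first eye (SAP 1.3), so age and first-eye preoperative BCDVA are both legitimate baseline covariates.

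**Balance.** Randomization is 1:1 and stratified by site (SAP 1.3). SAP 4 adds that, to ensure "comparable demographic characteristics between groups, statistical testing will be" performed. The visible text states no significance level and no action if a test is significant.

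**Other modelling.** Protocol 20.4 plans a mixed model for site and site-by-group effects. It addresses poolability and is not the decision test.

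**The concern.** The plan treats baseline comparability as important but pursues it with a tool that cannot deliver it. Under correct randomization the null hypothesis of a baseline test is true by construction. A significant result is therefore a chance finding, and a non-significant one does not remove a prognostic difference. With no action stated, the response to a significant result would have to be chosen after the data are seen.

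Meanwhile, whatever outcome variance age and preoperative acuity explain stays in the error term. If the groups differ by chance on either, part of that difference appears in the estimated lens effect of that particular trial. DCVA66 matters most here: it carries the claim of better intermediate vision and has less spare power than the primary endpoint.

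**Working it through.** **Inputs.** SAP 8 and Protocol 20.7 give 100 evaluable subjects per group. For BCDVA, SAP 8.1 works "at two-sided alpha of 0.10 with a non-inferiority margin of 1 line"; the true lens difference is set to zero and the SD to 1.2 lines. For DCVA66, SAP 8.2 gives a 0.8-line effect, SD 1.6 lines and one-sided alpha 0.025. One line is 0.1 logMAR. R², the share of 6-month outcome variance explained by age and preoperative BCDVA (r is its square root), is not in the documents. I assume 1% to 25% (r = 0.1 to 0.5).

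**Step 1: the plan's own power.** SE = SD × √(2/100).
- BCDVA: 1.2 × 0.1414 = 0.170 lines. Then 1/0.170 − 1.645 = 4.25, so power is about 99.999%. This agrees with the SAP's "there is over 90% power to conclude non-inferiority in visual acuity".
- DCVA66: 1.6 × 0.1414 = 0.226 lines. Then 0.8/0.226 − 1.96 = 1.58, so power is 94.2% by the normal approximation and 94.0% by noncentral t. This agrees with "there is over 90% power at one-sided 0.025 alpha to detect a 0.8-line or greater difference in mean visual acuity".

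**Step 2: DCVA66 with adjustment.** Residual SD = 1.6 × √(1 − R²); equivalent n per group = 100/(1 − R²); power by noncentral t.

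| Assumed R² | Residual SD (lines) | Power | Equivalent n per group |
|---|---|---|---|
| 0 | 1.600 | 94.0% | 100 |
| 1% | 1.592 | 94.2% | 101 |
| 5% | 1.559 | 95.1% | 105 |
| 10% | 1.518 | 96.0% | 111 |
| 25% | 1.386 | 98.2% | 133 |

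The half-width of the DCVA66 95% interval falls from 0.446 lines to 0.444 (R² = 1%) or 0.386 (R² = 25%). For the BCDVA 90% interval it falls from 0.280 to 0.279 or 0.243.

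**Step 3: chance imbalance.** The SE of a standardized baseline difference is √(2/100) = 0.141. The unadjusted lens difference shifts by r × SD × imbalance. For r = 0.1 to 0.5:
- One-SE imbalance (0.141): DCVA66 shifts by 0.023 to 0.113 lines, 3% to 14% of the 0.8-line effect.
- 1.96-SE imbalance (0.277, about one trial in 20 counting both directions): DCVA66 shifts by 0.044 to 0.222 lines, 6% to 28% of the effect. BCDVA shifts by 0.033 to 0.166 lines against a 1-line margin, and non-inferiority power stays above 99.9%.

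Among trials with a 1.96-SE imbalance favoring the test lens, the DCVA66 rejection rate under the null is 5.5%, 7.5% or 12.9% at r = 0.2, 0.3 or 0.5. With the imbalance running against the test lens, power is 88.7%, 85.0% or 75.4%.

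**Step 4: type I error over all randomizations.** In 100,000 simulated trials per setting, the unadjusted t-test at nominal 2.5% rejected in 2.51% (r = 0.3) and 2.48% (r = 0.5). The conditional rates in Step 3 average out.

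**Step 5: baseline tests.** SAP 4 names five characteristics. At an assumed 0.05 level and with independence, 1 − 0.95⁵ = 22.6%.

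**The case against.** The strongest reply is that nothing here is an error. A two-sample t-test in a 1:1 randomized trial is valid, and its confidence interval already allows for chance imbalance. That stands. A reader might infer from the Step 3 conditional rates that the plan inflates type I error or biases the comparison. It does neither: the rates describe a selected minority of trials, and Step 4 shows the overall error is kept.

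Second, the gain may be very small. Preoperative BCDVA is measured through the cataract that surgery removes, on a Snellen chart or equivalent, in eyes selected for good postoperative potential. It is also not a baseline value of DCVA66. Nothing in the documents supports the upper end of the assumed range. This stands as well, and is why the low end is the more likely.

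Third, the primary decision has so much power that adjustment cannot matter to it in practice. Agreed.

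Fourth, redaction. Text is blacked out after the DCVA66 criterion in Protocol 20.3 and after the mixed-model sentence in Protocol 20.4, and the SAP has gaps around the same endpoints. A reader might infer that no adjusted analysis is planned anywhere, or that baseline testing was chosen as a substitute for adjustment. The visible text supports neither. It shows only that the stated decision tests are unadjusted.

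Finally, no success criterion depends on the baseline tests, so a false positive there changes no formal decision. True, but it could still prompt unplanned analyses.

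**Conclusion.** The point holds as an inexpensive improvement, mainly for DCVA66, and not as a validity failure. The visible decision tests for both endpoints are sound but unadjusted, although usable covariates are collected before randomization. The benefit for DCVA66 lies between negligible (94.0% to 94.2% power) and worthwhile (98.2%), depending on a correlation that the documents do not give. For BCDVA only the interval width is affected.

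The wording in SAP 4 should change whatever the correlation turns out to be, because significance tests cannot secure balance. The figure of about 23% rests on five independent tests at a 0.05 level that the SAP does not state. Since SAP 4 uses Fisher's exact test for categorical data, which is conservative, the true rate is likely somewhat lower.

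**What to change.** Before unmasking:

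1. In SAP 5.1 and 5.2 and Protocol 20.3, base each decision on the lens-group difference from an ANCOVA with lens group, age, first-eye preoperative BCDVA in logMAR, and site as the stratification factor. SAP 2.4 already provides the Snellen-to-logMAR conversion. Leave the confidence levels, margin and significance thresholds as they are.
2. Name one glare condition for the preoperative BCDVA covariate. Protocol 10.3 accepts a value with or without glare, and the visible text does not guarantee that either is recorded for everyone. If no single condition is available for all subjects, adjust for age and site only.
3. State a simple rule for missing covariate values.
4. Keep the unadjusted t-test as a sensitivity analysis.
5. In SAP 4, replace the significance tests with descriptive summaries by lens group.

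Cost: wording and one model per endpoint, with no additional subjects. With the full 15 sites, site uses 14 degrees of freedom and the covariates 2, leaving 200 − 1 − 1 − 2 − 14 = 182 for error instead of 198. The two-sided 95% critical value moves only from 1.972 to 1.973.
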